**1. Purpose of the surveillance**

This postmarketing surveillance of Humira® for Subcutaneous Injection (generic name: adalimumab (recombinant)) will be conducted to clarify the following with regard to the treatment of juvenile idiopathic arthritis (JIA) affecting multiple joints with this drug:

- ① Unknown adverse drug reactions (ADRs) (especially important ADRs)
- ② Incidence and conditions of occurrence of adverse reactions in the clinical setting
- ③ Factors that may affect the safety and efficacy of Humira

< Items of investigation of particular interest>

Development of infections, tuberculosis, malignant tumor, administration site reactions, autoimmune diseases, pancytopenia, demyelinating disease, congestive heart failure, and interstitial pneumonia

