**2. Target number of patients**

Target sample size: 100 patients

Immediately after the approval of JIA as an indication for treatment with Humira, all patients who receive Humira for the treatment of JIA affecting multiple joints will be registered, and the data for the first 100 patients will be tabulated and analyzed, and the results reported to the regulatory authority. Registration of patients will be continued until the authority concludes its final evaluation.

<Rationale>

Considering the number of patients for whom registration is considered feasible, we will analyze data for 100 patients to detect ADRs with an incidence of 3% at a probability of 95%.

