#### 9.14. Level of significance

In principle, the significance level of statistical analyses used in this survey is two-sided 5%.  $p < 0.05$  ( $< 5\%$ ) should be considered significant.

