Administration by a doctor	In “2. Status of Humira treatment” in the registration form, administration is “administration by a doctor” at all timings.
Dosage and administration category: Dose increase group (20 mg → 40 mg)	In “2. Status of Humira treatment” in the registration form, “dose” was increased from 20 mg to 40 mg.
Dosage and administration category: Maintained dose group	In “2. Status of Humira treatment” in the registration form, “dose” was never increased or reduced.
Dosage and administration category: Other	In “2. Status of Humira treatment” in the registration form, “dose” was reduced to below 20 mg, “dose” was increased from 40 mg to 80 mg, “dose” was increased and then reduced, or “number of doses” is other than biweekly.
Patients deviated from	Patients who received Humira at a dose other than “20 mg/2 weeks”

Name of data	Derivation and calculation methods
recommended dosage and administration of Humira	or “40 mg/2 weeks” are defined as patients deviated from the recommended dosage and administration.
Previous medications	Of the drugs listed under “Status of administration of concomitant drugs” in “5. Previous medications for juvenile idiopathic arthritis” in the CRF and confirmed to have been administered between the start date of Humira treatment - 90 days and the start date of Humira treatment - 1 day, drugs falling under “MTX”, “DMARDs”, “steroid (oral + injection)” or “NSAIDs (oral + injection)” in “Drug code list_20171012.xlsx” are defined as previous medications.
Status of previous medications	“With previous medications” should be selected when the patient was previously treated with medications, “unknown/unspecified” should be selected when “Status of previous medications for juvenile idiopathic arthritis” is not specified or indeterminable, and “without previous medications” should be selected otherwise.
Previous medication: Methotrexate	“With previous medication: methotrexate” should be selected when the conditions for “previous medications” are met and the previous medication falls under “MTX” in “Drug code list_20171012.xlsx”, “unknown/unspecified” should be selected when the status of previous medications is “unknown/unspecified”, and “without previous medication: methotrexate” should be selected otherwise.

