Data	Layer separation
disorder	
Complication: Cardiovascular disorder	No, yes, unknown/unspecified
Complication: Blood disorder	No, yes, unknown/unspecified
Complication: Respiratory disorder	No, yes, unknown/unspecified
Complication: Other	No, yes, unknown/unspecified
History of allergy	No, yes, unknown/unspecified
Breakdown of history of allergy	Drug, food, other
Previous medications	No, yes, unknown/unspecified
Breakdown of previous medications	Methotrexate, corticosteroid, NSAIDs, other DMARDs
History of treatment with previous medications (biological products)	No, yes, unknown/unspecified
Breakdown of history of treatment with previous medications (biological products)	Tocilizumab, etanercept, other
Concomitant drugs	No, yes, unknown/unspecified
Breakdown of combination drugs	Methotrexate, corticosteroid, NSAIDs, other DMARDs, other drugs
Tuberculin skin test	Tested, not tested, unknown/unspecified
Quantiferon test (including T-SPOT)	Tested, not tested, unknown/unspecified
Chest x-ray	Tested, not tested, unknown/unspecified
Chest CT	Tested, not tested, unknown/unspecified
Immunology test (tuberculin skin test or Quantiferon test or T-SPOT)	No, yes, unknown/unspecified
Image testing (chest x-ray or chest CT)	No, yes, unknown/unspecified
Prophylactic administration (status of prophylactic administration by	No, yes, unknown/unspecified

Data	Layer separation
implementation status of tuberculosis tests)	
HBs antigen test	Implemented (negative, positive, unknown/unspecified, subtotal), not implemented, unknown/unspecified
HBs antibody test	Implemented (negative, positive, unknown/unspecified, subtotal), not implemented, unknown/unspecified
HBc antibody test	Implemented (negative, positive, unknown/unspecified, subtotal), not implemented, unknown/unspecified
Status of Humira treatment (dosage and administration)	20 mg/2 weeks, 40 mg/2 weeks, 20 mg/2 weeks → 40 mg/2 weeks, other
Number of doses	≥1 to <2 doses, ≥2 to <6 doses, ≥6 to <12 doses, ≥12 doses
Days to the date of the last dosing	1 to 28 days, 29 to 84 days, 85 to 168 days, ongoing at day 169
Dose at the start of Humira treatment	20 mg, 40 mg, 80 mg, other, unknown/undescribed
Dosage and administration category	Dose increase group (20 mg → 40 mg), maintained dose group, other, unknown/unspecified
Self-administration	No, yes, unknown/unspecified
Error caused by self-administration	No, yes, unknown/unspecified

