#### “Table 2.9 Incidence of adverse reactions in patients who received an increased dose”

Analysis object: Patients included in the safety analysis set

Purpose of analysis: Adverse reactions during the safety analysis period will be aggregated in accordance with “11. Data-layer separation” (dosage and administration category) as shown below. The number of patients analyzed, the number and percentage of patients who experienced adverse reactions, the number of adverse reactions, the number of patients who experienced adverse reactions

by type of adverse reaction (by SOC and PT) and their percentages against the patients analyzed will be calculated.

Number of patients who experienced adverse reactions: Number of patients who experienced adverse reactions.

Number of adverse reactions: Number of adverse reactions that occurred. When a single patient experienced multiple episodes of the same adverse reaction (PT), they should be counted as one event.

Types of adverse reactions: Should be calculated by SOC and by PT. Output data should be sorted in the order of international agreements and in the ascending PT code order. When a single patient experienced multiple episodes of the same adverse reaction (PT), they should be counted as one event.

Note: The version of MedDRA/J used should be provided.

“Table 2.10 Incidence of adverse reactions in patients who self-administered Humira”

Analysis object: Patients included in the safety analysis set

Purpose of analysis: Adverse reactions during the safety analysis period will be aggregated in accordance with “11. Data-layer separation” (self-administration) as shown below. The number of patients analyzed, the number and percentage of patients who experienced adverse reactions, the number of adverse reactions, the number of patients who experienced adverse reactions by type of adverse reaction (by SOC and PT) and their percentages against the patients analyzed will be calculated.

Number of patients who experienced adverse reactions: Number of patients who experienced adverse reactions.

Number of adverse reactions: Number of adverse reactions that occurred. When a single patient experienced multiple episodes of the same adverse reaction (PT), they should be counted as one event.

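### No planned summary table of safety or efficacy is broken down by Humira dose level, and Table 2.9 pools constant 20 mg and constant 40 mg patients

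*SAP*

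**What the plan says.** Protocol section 1 gives as its third purpose to clarify "Factors that may affect the safety and efficacy of Humira", and SAP 4.1 repeats it. Protocol section 9(1) plans adverse drug reactions and efficacy by patient background factor, and reactions before and after an increase in Humira dose.

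SAP Tables 2.5.1 (adverse reactions), 3.1 (DAS28 remission) and 3.5.2 (EULAR response) use the same list of 32 factors and test 31 of them; disease type is not tested. Concomitant methotrexate appears both as yes/no and by dose band. No Humira dose item appears.

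SAP Section 11 does define Humira dose layers. One is the starting dose: "20 mg, 40 mg, 80 mg, other, unknown/undescribed". Another separates patients on 20 mg, on 40 mg, raised from 20 to 40 mg, and other.

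Table 2.9 uses neither of these. It reports reactions by the dosage and administration category of SAP 10.1: raised from 20 to 40 mg, maintained, other, unknown. A maintained dose is one that "was never increased or reduced", whatever its level. The category for other takes in a dose that "was increased from 40 mg to 80 mg", together with reductions below 20 mg, increases later reversed, and dosing that is not every two weeks.

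**The concern.** Dose is an obvious candidate when looking for factors that bear on safety and response. Here the dose of a concomitant drug is tabulated against outcomes and the dose of the surveyed drug is not. Table 2.5.5.X does not close the gap, because it takes up only factors found significant in Table 2.5.1.

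In Table 2.9 the natural comparator for the 20 to 40 mg group is the maintained row. If reaction rates differ by dose level, that row's rate depends on how many patients happened to be on each dose. A gap between it and the increase group could then come from the mix alone. The category for other adds increases to reductions, so its rate has no clear direction.

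**Working it through.** **1. The plan's own figure.** Protocol section 2 states "Target sample size: 100 patients", chosen to detect a reaction of 3% incidence with 95% probability. The chance of at least one case is 1 − 0.97^100 = 0.952, and the smallest adequate n is ln 0.05 / ln 0.97 = 98.4, so 99. The figure reproduces. It is a whole-group figure and is not in dispute.

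**2. Where the dose layers are used.**

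| SAP Section 11 layer | Levels | Tables | Outcome reported? |
|---|---|---|---|
| Humira treatment status | 20 mg, 40 mg, 20 to 40 mg, other | 1.8 | No |
| Humira starting dose | 20, 40, 80 mg, other, unknown | 1.10, crossed with body weight | No |
| Dosage and administration category | raised 20 to 40 mg, maintained, other, unknown | 2.9 | Adverse reactions only |
| Methotrexate dose per m² (for comparison) | four bands, unknown | 2.5.1, 2.11, 3.1, 3.5.2 | Yes |

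The two layers that separate dose levels reach no outcome table. The one layer that reaches an outcome table does not separate dose levels. No efficacy table uses Humira dose or dose change.

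**3. What pooling does.** The documents give neither the dose split nor rates by dose, so these inputs are assumptions: 80 maintained patients, with reaction rates of 20% on 20 mg and 40% on 40 mg.

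Maintained rate = (n20 × 0.20 + n40 × 0.40) / (n20 + n40)

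- 20:60 gives (4 + 24)/80 = 35%
- 40:40 gives (8 + 16)/80 = 30%
- 60:20 gives (12 + 8)/80 = 25%

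An increase group at 30% would look lower than, equal to or higher than the maintained row, depending only on the split.

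**4. How far body weight stands in.** Weight classes (<15, 15 to <30, ≥30 kg) appear in Tables 2.5.1, 2.7, 3.1 and 3.5.2.

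- If, as an assumption, every patient of 15 to <30 kg had 20 mg and every patient of ≥30 kg had 40 mg, the weight rows would themselves read 20% and 40%. Table 1.10 would show the correspondence.
- If a class held both doses equally, its row would read 0.5 × 20% + 0.5 × 40% = 30%.
- Dose per kg varies within a class. At 20 mg it runs from 20/15 = 1.33 mg/kg down to just above 20/30 = 0.67 mg/kg across the 15 to <30 kg class.

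Weight is therefore an indirect proxy, good or poor according to how closely dose follows it. The documents state no such rule.

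**5. What dose strata could show.** Assume 100 patients, all on one of two starting doses, tested with Fisher's exact test at two-sided 0.05. Power is the sum of the binomial probabilities of all tables with p < 0.05. The chance of seeing a 3% reaction at least once in a stratum is 1 − 0.97^n.

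| Split | 3% reaction seen, each stratum | Power, 20% v 30% | 20% v 40% | 20% v 50% |
|---|---|---|---|---|
| 20:80 | 46% / 91% | 9% | 35% | 70% |
| 30:70 | 60% / 88% | 12% | 46% | 82% |
| 50:50 | 78% / 78% | 16% | 52% | 85% |

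Only large differences would be found with reasonable probability.

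**The case against.** The protocol promises less than a dose-level comparison. Its factor analyses are by patient background, and its one named dose analysis concerns events before and after an increase. Table 2.9 is a dose-change table with no planned test. On this view, dose strata are a sensible addition but no commitment has been broken. That stands, and it keeps the point modest. It does not remove it, because the general purpose covers factors for both safety and efficacy, and a methotrexate dose breakdown was thought worth planning.

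A reader might go further and infer that the survey cannot say anything about dose. The documents do not support that. Table 4.2 lists body weight, initial and maximum dose, adverse events with causality, and effectiveness for each patient. Table 4.4 lists maximum and mean dose with reactions and remission, and Table 4.3.2 itemises dose changes. A dose-level table could be built from these, although it would then be an unplanned one.

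Nor can it be said that a dose difference would appear nowhere, or that weight class carries no information on mg/kg. Step 4 shows that the weight rows could reproduce a dose difference exactly. Equal mg/kg ranges in two classes would not mean equal distributions.

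The low power in step 5 and possible confounding by weight also stand. They limit how the added rows may be read. They apply in kind to the factors already tested, so they are no reason to leave dose out.

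**Conclusion.** The point holds as a gap in the planned summary tables. Humira dose level is in none of the aggregated safety or efficacy tables, and Table 2.9 mixes constant 20 mg with constant 40 mg. Differences between dose levels will not be directly visible in those tables, although the data are collected and listed by patient.

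The size is illustrative only. Under assumed rates of 20% and 40%, the maintained row moves between 25% and 35% with the mix. Power to detect that difference once the doses are separated is about 35% to 52% at N = 100. Registration continued beyond the first 100, so the final number may differ.

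A reader might also infer that splitting the maintained row would isolate the effect of raising the dose. It would not. Dose was not randomised, patients must stay on treatment long enough to be increased, and Table 2.9 does not place events before or after the increase. This is an inexpensive improvement to reporting, not a flaw that invalidates the survey.

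**What to change.** 1. Add the starting-dose layer already in SAP Section 11 to the factor lists of Tables 2.5.1, 3.1 and 3.5.2, labelled exploratory. Show it within body-weight class wherever both doses occur. Starting dose per kg of baseline weight is an optional further factor.
2. In Table 2.9, replace the maintained row by three rows: constant 20 mg every two weeks, constant 40 mg every two weeks, and other constant dose. The 20 to 40 mg group can then be set beside each dose level.
3. Give every patient exactly one row. As SAP 10.1 stands, a constant dose not given every two weeks fits both maintained and other, and a change from 40 to 20 mg fits no category.
4. Optionally, show increases and reductions separately within the category for other.

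These changes concern reporting categories only and imply nothing about which dose should be used. The cost is SAP wording and a few table rows, since dose and weight are already collected. The downside is a few more low-powered comparisons added to the 31 tests per table, possibly confounded by weight. They should be read descriptively and not as the effect of a dose increase.

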#### **2) Information on the safety of Humira**

- ① List of adverse drug reactions (ADRs)/infections
- ② Factors which may affect the safety of Humira
  - Incidence of ADRs by patient background factor
  - Incidence of ADRs before and after increase in Humira dose
- ③ Adverse events occurring during or after the treatment period
  - List of occurrences of serious adverse events
- ④ Errors in administration during self-injection

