Footnotes	
Where it is considered necessary to provide an explanation in association with preparation of analysis results, provide the explanation in a footnote.
 
Footnotes should be in the following form:
 
Add a superscript “*sequential number” on the right side of a term, etc. that you want to explain, and provide the “*sequential number” corresponding to the footnote and the explanation under the diagram.

Percentage	
When a percentage is calculated, the denominator should be the number of patients in the analysis set.
 
*Specify in a footnote when the denominator used for calculation of a percentage in the same table is different from the number of patients in the analysis set.
 
When percentages for a breakdown of a factor or item are calculated, ensure that the total becomes 100%. Any item redundantly counted should be specified in a footnote.

Context of numbers	When a figure such as a patient composition figure is created, all numbers required to maintain consistency of the context of numbers should be provided.

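### The dosage categories behind SAP Table 2.9 overlap and leave gaps, so membership of the dose-increase group probably depends on what happened after the increase

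*SAP*

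**What the plan says.** SAP 10.1 defines three dosage and administration categories:

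- **Dose increase group**: "dose” was increased from 20 mg to 40 mg". Nothing is said about later changes.
- **Maintained dose group**: "dose” was never increased or reduced". Nothing is said about the dosing interval.
- **Other**: a reduction to below 20 mg, an increase from 40 to 80 mg, or a patient whose "dose” was increased and then reduced, or “number of doses” is other than biweekly".

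SAP section 11 lists the layers as "Dose increase group (20 mg → 40 mg), maintained dose group, other, unknown/unspecified", with no order of precedence.

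Table 2.9 is titled "Incidence of adverse reactions in patients who received an increased dose", and its instruction is: "Adverse reactions during the safety analysis period will be aggregated in accordance with “11. Data-layer separation” (dosage and administration category) as shown below". Its only note concerns the MedDRA/J version.

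Two other places bear on the point. SAP 9.10 says: "When percentages for a breakdown of a factor or item are calculated, ensure that the total becomes 100" per cent, and it requires a footnote wherever an item is counted more than once. Protocol section 9, under safety information, names this analysis: "Incidence of ADRs before and after increase in Humira dose".

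**The concern.** A programmer who applies the three definitions as written will find patients who belong to two groups and patients who belong to none. Nothing in 10.1, section 11 or Table 2.9 says what to do with them, so two programmers could produce different tables from the same data.

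Table 2.9 is the only SAP table that aggregates reactions by dose increase, and dosage category is not among the background factors in Table 2.5.1. If Other takes precedence, a patient raised to 40 mg and later changed again leaves the increase group, while one who stays at 40 mg remains. The group would then be conditioned on an event after the exposure of interest, under a title that promises all patients who received an increased dose.

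**Working it through.** The plan states no figure on this point to reproduce. The check is to apply the 10.1 definitions literally to possible dose courses, and then to see what reassignment could do.

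**Step 1: classification.** Dosing is biweekly unless stated.

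| Course (mg) | Dose increase | Maintained | Other |
|---|---|---|---|
| constant 20 or constant 40 | – | yes | – |
| 20→40 | yes | – | – |
| 20→10, or 40→80 | – | – | yes |
| 20→40→20 | yes | – | yes |
| 20→40→80 | yes | – | yes |
| 20→40, not biweekly | yes | – | yes |
| constant 20, not biweekly | – | yes | yes |
| 40→20 | – | – | – |
| 80→40 | – | – | – |
| 10→20 | – | – | – |

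Four courses fall in two groups and three fall in none. The last three are known courses, so the unknown/unspecified layer does not fit them either.

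**Step 2: which resolution is likely.** If *s* patients were counted in two rows, and all others in one, the rows would add to N + *s*. With N = 100 (the target) and *s* = 2 or 4, that is 102 or 104. SAP 9.10 asks for breakdowns that total 100% and for a footnote on redundant counts. Tables that allow overlap, such as 1.1, 1.2 and 2.5.2, say so in their notes; Table 2.9 does not. Keeping such a patient only in the increase group would go against the explicit clause on doses raised and then lowered. Moving the patient to Other is therefore the likeliest reading.

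**Step 3: effect on incidence.** Let *n* patients ever have the 20→40 mg step, *k* of them with a reaction. Let *s* move to Other, *t* of them with a reaction. The incidence changes from *k*/*n* to (*k* − *t*)/(*n* − *s*). It falls only if *t*/*s* exceeds *k*/*n*, that is, if those who move react more often than those who stay.

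The documents give none of these counts. With *n* = 20 and *k* = 6 assumed (6/20 = 30.0%):

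- *s* = 2, *t* = 2: (6 − 2)/(20 − 2) = 4/18 = 22.2%
- *s* = 4, *t* = 4: (6 − 4)/(20 − 4) = 2/16 = 12.5%
- *s* = 4, *t* = 1: (6 − 1)/(20 − 4) = 5/16 = 31.25%

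In the third case *t*/*s* = 25%, below 30%, and the incidence rises slightly.

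**The case against.** The best defence is that the intention can be inferred. The clauses on an increase followed by a reduction, and on 40 to 80 mg, look written to take such courses out of the increase group. Table 1.8 likewise sends every regimen outside its three named ones to other. A clean-regimen group beside a mixed group is a legitimate descriptive choice. Table 2.9 is descriptive and carries no test. Nothing is hidden: moved patients appear under Other with their reactions by SOC and PT, Table 4.3.2 lists each dose change with its reason, Table 4.3 flags patients who received an increased dose, and Table 4.2 gives onset dates and causality. In a survey planned for 100 patients, regrouping from the listings is feasible.

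Most of this stands, and it limits the harm. It does not supply the missing rule. Table 1.8 concerns a separate variable with different layers. The Table 4.3 flag has no definition in 10.1, so listing and table could disagree. The courses that fit no group remain unassigned.

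A reader might go further and infer that the rule removes patients *because* they reacted, so that the incidence is biased towards zero. The documents do not support that. Reassignment follows from the dose course, whatever the reason for the change, and no passage ties a reduction to a reaction. A reader might also infer that patients will be counted twice; SAP 9.10 and the absence of a redundancy note speak against it.

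**Conclusion.** The defect is real and modest. The categories used in Table 2.9 are neither mutually exclusive nor exhaustive, and no precedence rule repairs them. Under the likeliest reading, membership of the increase group depends on a later event. Its reaction incidence can then be biased: downward if patients who move react more often than those who stay, otherwise little changed or upward. Neither direction nor size can be determined from the documents; the range of 12.5% to 31% against 30% rests wholly on assumed counts. Reactions of moved patients are misplaced within the table, not lost.

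A related gap sits in the same table. The protocol asks for incidence before and after the increase, whereas Table 2.9 pools all reactions in the safety analysis period.

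**What to change.** Amend SAP 10.1 and Table 2.9 so that each patient falls in exactly one group:

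- **Dose increase**: any patient with a 20→40 mg step, with sub-rows for those maintained after the increase and those later changed again.
- **Maintained**: constant dose, given biweekly throughout.
- **Other**: the residual, for all remaining known courses, including 40→20 mg.
- **Unknown/unspecified**: kept as it is.

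Within the increase group, split reactions by onset before or after the increase, as the protocol asks. Because Table 2.9 counts a repeated PT once per patient, state how a PT that occurs on both sides is placed. Use the same definition for the increased-dose flag in Table 4.3.

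The cost is SAP wording and a few table rows; doses, reasons for dose changes and onset dates are already collected. The downside is a slightly more heterogeneous increase group, which the sub-rows make visible. This concerns analysis grouping only and implies nothing about how patients should be dosed.
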